3 INVESTIGATION PLAN

3.1 Study Design

3.2 This is a randomized open label trial that will compare the safety and efficacy of PA and AL in patients of both sexes between the ages of 3 months and 10 years who have symptomatic microscopically confirmed acute uncomplicated *Plasmodium falciparum* malaria. Patients will be randomized following a pre-generated randomization code. On the basis of the results of these assessments, the patients will be classified as having therapeutic failure (early or late) or adequate clinical and parasitological response (ACPR). The proportion of patients experiencing therapeutic failure during the follow-up period will be used to estimate the efficacy of the study drug(s). The primary outcome will be PCR-adjusted adequate clinical and parasitological response (ACPR) i.e., absence of patent parasitaemia, regardless of axillary temperature and without evidence of previous treatment failure up to day 28. Secondary outcomes will be adequate clinical and parasitological response without correction for reinfection, parasite clearance time, fever clearance time and the proportions of patients who are aphasitaemic or afebrile on days 1, 2, and 3.

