3.6.1 Inclusion criteria

- Individuals of either gender between the ages of 3months (but weight ≥ 5 kg) and 12 years who present with symptoms compatible with acute uncomplicated malaria
- Minimum asexual parasite density of $1000/\mu\text{l}$. This will be done at enrolment for all study participants.
- Fever with an axillary temperature $\geq 37.5^{\circ}\text{C}$ or history of fever within 24hours of presentation
- Residence within 15 kilometers to study site
- Ability to take drugs orally
- Absence of history of ACT intake in the two weeks prior to enrolment
- A signed informed consent from parents or guardian of prospective enrollee to participate in the study

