3.7.5 Follow-up of Adverse Events

The healthcare personnel must take all appropriate measures to protect the safety of the patients. Personnel must ensure to document follow-up of the evolution of each adverse event (clinical, biological or other) until resolution or until the stabilization of the patient's status.

All new relevant information concerning the initial SAE shall be recorded on a form "SAE follow-up information form" by the nursing staff of the health centre, and shall be validated by the PI/co-PI who shall transfer the form to the local person/physician responsible for the pharmacovigilance of the project and Shin Poong PV.

In case of a serious adverse event the patient must be followed until complete resolution and normalization of all analysis results, or until chronicity of the patient's status. This can imply that the follow-up of the patient must continue beyond the period of follow-up per protocol, and that additional investigations could be requested.

DATA ANALYSIS.

Data will be entered into the computer using the Epi-data software. This subsequently would be cleaned and transferred to SPSS Statistic Software version 20 for analysis. The outcome of interest (dependent variable) presented as a categorical variable with, presence of malarial parasitemia, and the level of efficacy reported. The independent or explanatory variable of interest in this study would be use of chemotherapy. All independent variable would be reported as categorical. Proportions of treatment outcome will be compared by using chi square. Normally distributed continuous data will be compared using unpaired student t-test. Mean values will be given as mean \pm SD and values of $P < 0.05$ will be considered statistically significant.

ETHICAL CONSIDERATIONS

This study, will be a prospective randomized open label clinical trial comparing the safety and efficacy of Pyronaridine-artesunate and Artemether-lumefantrine in the treatment of symptomatic acute uncomplicated malaria in Nigerian children aged 3 to 144 months who seek treatment in the study hospital. The studies will be conducted according to Good Clinical Practice and the Declaration of Helsinki.

Confidentiality of data: Personal details of enrollees in the study will be treated with utmost confidentiality, as it is against the principles of good clinical practice to make such information public. Also, codes will be assigned to all participants.

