Address (+ brief description):
.....
.....
.....

Symptoms History

Record duration of symptoms in days (Today = 1) Fever: () Vomiting: () Chills & rigors ()

Diarrhoea: () Headache: () Abdominal pains: () Irritability: () Loss of appetite ()

Other complaint 1: Other complaint 2:

Past medical history:

History of drug allergy: (Yes/No) If yes, name of drug:

Any other relevant history 1:

Any other relevant history 2:

Treatment history: Has the child received any of the following drugs in the last 2 weeks (Yes/No)

CQ () SP () PCM () ACT () Specify.....

Antibiotic () Specify..... Other:

Clinical examination:

General: Palor (Yes/No) Icterus (Yes/No) Fever (Yes/No) Dehydration (Yes/No)

CVS: Pulse/min..... Apex Beat..... Heart sounds.....

Respiratory system: Resp. rate..... Breath sound.....

Abdomen: Liver size (Below costal margin)..... Spleen size..... Kidneys.....

Muscle tone: (1) Normal (2) Hypotonia (3) hypertonia Eyes: conjunctivitis/Discharge (Yes/No)

Ears: Discharge (Yes/No)

MP result: PCV.....

**PYRONARIDINE-ARTESUNATE VERSUS ARTEMETHER-
LUMEFANTRINE STUDY**

Study ID- PAAL:

Study ID -----

Study Drug Schedule

| Study Day | Date | Drug [PA or AL] Name of Drug | Dose | Time Drug Given |
|------------------|-------------|---|-------------|------------------------|
| Day 0 | | | 1st | |
| | | | 2nd | |
| Day 1 | | | 1st | |
| | | | 2nd | |
| Day 2 | | | 1st | |
| | | | 2nd | |

Comments:

Any vomiting? Yes/No

Time

Any Redosing?

Time

Any vomiting? Yes/No

Any other comments

CLINICAL FOLLOW UP RECORD

| | D0 | D1 | D2 | D3 | D7 | D14 | D21 | D28 | Day 35 | Day 42 | Other visit |
|---------------------------|-----------|-----------|-----------|-----------|-----------|------------|------------|------------|---------------|---------------|--------------------|
| Date | | | | | | | | | | | |
| Temp (°C) | | | | | | | | | | | |
| Pallor | | | | | | | | | | | |
| Jaundice | | | | | | | | | | | |
| HR/Pulse Rate | | | | | | | | | | | |
| Resp Rate | | | | | | | | | | | |
| Lung Fields | | | | | | | | | | | |
| Liver (cm) | | | | | | | | | | | |
| Spleen (cm) | | | | | | | | | | | |
| Weight (kg) | | | | | | | | | | | |
| PCV (%) | | | | | | | | | | | |
| Parasite Density/ μ L | | | | | | | | | | | |
| Gametocyte Count/ μ L | | | | | | | | | | | |

TREATMENT EMERGENT SIGNS AND SYMPTOMS (TESS)

| Features | Day 0 | | Day 1 | | Day 2 | | Day 3 | | Day 7 | | Day 14 | | Day 21 | | Day 28 | | Day 35 | | Day 42 | | Extra Visit | | Extra Visit | | |

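### Day 1 and Day 2 aparasitaemia are compared without using Day 0 parasite density, which is recorded for every child: a valid test, but with some precision given away

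*Combined protocol and SAP*

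**What the plan says.** - **Endpoint.** The Study Design section (3.1/3.2) lists, among the secondary outcomes, "the proportions of patients who are aphasitaemic or afebrile on days 1, 2, and 3". This point concerns the parasite part (aparasitaemic, yes or no).
- **Test.** The Data Analysis section says "Proportions of treatment outcome will be compared by using chi square", and that values of P below 0.05 "will be considered statistically significant".
- **Explanatory variables.** The same section says "The independent or explanatory variable of interest in this study would be use of chemotherapy", followed by "All independent variable would be reported as categorical". No covariate model or stratified analysis appears anywhere.
- **Day 0 density.** Section 3.6.1 sets a "Minimum asexual parasite density of" 1000/µl and adds "This will be done at enrolment for all study participants". The case record form has a "Parasite Density" row whose columns begin at D0. Neither section 3.6.1 nor section 3.6.2 gives a maximum. The severe-malaria exclusion is clinical and carries no density figure.
- **Randomisation.** A pre-generated code is used. No stratification by density is stated.

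**The concern.** Under section 3.7.2 a slide is read against 500 leukocytes before it is called negative. A negative smear therefore means that density has fallen below a roughly fixed detection limit. How soon that happens depends on the starting density as well as on the speed of the drug. Entry densities can differ by orders of magnitude, and neither the randomisation nor the analysis takes account of this.

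Day 0 density is fixed before treatment, so adjusting for it cannot introduce post-treatment bias. Leaving it out keeps explainable variation in the comparison of how fast the two drugs act. At stake is the precision of a secondary comparison, and how comfortably one realised trial can be interpreted if the arms happen to start at different densities.

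**Working it through.** **1. The plan's own figure.** The documents give no sample size or power for this endpoint. The only figure is for the primary outcome (section 3.6):

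n = (z_α + z_β)² × [P1(1−P1) + P2(1−P2)] / [ε − (P1−P2)]²

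The variance term is 0.964×0.036 + 0.989×0.011 = 0.04558. The denominator is (0.05 + 0.025)² = 0.005625. With one-sided 5% (z = 1.645), n is 70 per group at 90% power and 51 at 80%, as printed. The z of 1.96 printed there would give 86 and 64, which is a separate matter. I use 84 per arm (randomised) and 70 per arm (evaluable).

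**2. Why starting density matters.** Assumptions, none from the documents: 3 h lag and a lognormal half-life with median 2.5 h and log-scale SD 0.3. From section 3.7.2: 500 leukocytes at 8,000/µl, so one parasite seen corresponds to 8,000/500 = 16/µl.

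At 24 h a child with the median half-life has had (24−3)/2.5 = 8.4 halvings, a factor of 2^8.4 ≈ 338.
- From 1,000/µl: 1,000/338 ≈ 3.0/µl, or 3.0/16 ≈ 0.19 parasites expected on the slide. The chance of seeing none is exp(−0.19) ≈ 0.83.
- From 200,000/µl: about 592/µl, or 592/16 = 37 parasites expected. The slide is positive.

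Averaged over the spread of half-lives, Day 1 aparasitaemia is about 73% at 1,000/µl and 5% at 200,000/µl.

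**3. Power with and without adjustment.** Further assumptions: log10 Day 0 density normal with mean 4.3, truncated at 3; PA shortens the half-life by 13%. Simulation: 3,000 trials per setting, 84 per arm, chi-square against a likelihood-ratio test adjusted for log10 density, Day 1.

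| SD of log10 density | Chi-square | Adjusted | Gain (points) |
|---|---|---|---|
| 0.5 | 45.0% | 49.8% | 4.8 |
| 0.7 | 42.1% | 47.9% | 5.8 |
| 0.9 | 38.3% | 45.4% | 7.1 |

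Repeat runs move these by a point or two, so the Day 1 gain is about 4 to 7 points. At 70 per arm power goes from 38 to 43%, 36 to 42% and 32 to 38%. Under no treatment difference both tests rejected at about 4 to 6%.

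The later days under the same model, 84 per arm:
- **Day 2:** 88–91% clear on artemether-lumefantrine (AL) and 94–96% on PA. Power is about 22–25% unadjusted and 26–28% adjusted, a gain of about 2 to 5 points.
- **Day 3:** about 99% clear on AL and over 99.5% on PA. With 99.8% clear on PA, the chance of no parasitaemic child in that arm is 0.998^84 ≈ 0.85. Counting either arm, it happens in roughly 81–95% of trials.

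**4. A second model, without kinetics.** 70 per arm, 2,000 trials per setting. OR is the assumed odds ratio for still being parasitaemic per SD of log Day 0 density. Entries are the cut in the variance of the risk difference from adjustment.

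| Clear, arm v arm | OR 1.5 | OR 2 | OR 3 |
|---|---|---|---|
| 30% v 50% | 4% | 6% | 18% |
| 50% v 70% | 3% | 11% | 20% |
| 80% v 92% | 2% | 4% | 13% |
| 95% v 99% | about 0–1% | about 0–1% | about 0–1% |

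At 50% v 70%, power goes from 0.70 to 0.72, 0.68 to 0.73 and 0.67 to 0.77. With OR 1 there is no gain.

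**5. Chance imbalance.** The SD of the between-arm difference in mean log density, in SD units, is √(2/n): √(2/84) = 0.154 and √(2/70) = 0.169. The chance of an imbalance above 0.25 SD is 10.5% and 13.9%. At 50% v 70% clear and 70 per arm, such an imbalance moves the unadjusted risk difference by 2.4, 3.9 or 5.4 points for OR 1.5, 2 or 3. The standard error of that difference is about 8 points. With no true difference (50% v 50%), the unadjusted test rejected in 4.6–5.3% of simulated trials.

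**The case against.** The strongest reply is that nothing here is wrong. In a randomised comparison the unadjusted chi-square is valid, and the null runs confirm it. A reader might infer that a chance difference in Day 0 density would bias the result or be mistaken for a difference in drug speed. That goes too far: such differences are part of the 5% error rate that the test already controls. This part of the reply stands.

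A reader might also infer that the sentence on categorical variables itself costs precision. The documents do not support that. The only explanatory variable named is treatment, which is categorical anyway; the verb is reported; and there is no covariate model for the sentence to damage. It matters only if density is added later and the sentence is then read literally.

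Third, a reader might extend the remedy to all three days. On Day 3 a logistic model would usually have an arm with no parasitaemic child, so the arm coefficient would have no finite estimate.

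Two smaller points also stand. The plan does not explicitly assign a test to this endpoint: elsewhere, treatment outcome means the failure and response categories, so the chi-square is inferred as the only method given for proportions. And the endpoint is absent from the objectives in section 2.1 and has no power claim. What survives all this is that a baseline predictor already collected is left unused where it would help.

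**Conclusion.** The point holds as one of efficiency, not validity. The plan makes no use of Day 0 density in comparing early aparasitaemia, although every child has the value and entry sets no upper limit. Under the assumed kinetics, adjustment adds about 4 to 7 points of power on Day 1, about 2 to 5 on Day 2 and almost nothing on Day 3. In the second model the variance falls by about 2 to 20% while a material share of children are still parasitaemic.

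The half-life, lag, density distribution, treatment effect and predictive strength are all assumptions. If density predicts clearance weakly, the gain shrinks towards nil. The primary outcome and its sample size are unaffected. This is a free improvement of low consequence.

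**What to change.** Add to the Data Analysis section:

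- For aparasitaemia on Days 1 and 2, fit a logistic regression on treatment arm and continuous log10 Day 0 parasite density. Report the standardised risk difference with its 95% interval, and show the unadjusted comparison beside it.
- For Day 3, or whenever an arm has few or no parasitaemic children, report the unadjusted risk difference with an exact or score interval. Fix the count that triggers this before the data are examined.
- Use the same covariate in any model for parasite clearance time.
- State that the sentence on categorical independent variables does not apply to this covariate.

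The cost is analysis wording only: no new data, visits or participants, and no change to the entry criteria. The wording should be settled in advance, because in an open-label trial an adjustment chosen after an imbalance has been seen is open to challenge.

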3.3 Study Site

The study will be conducted in Oni Memorial Children's Hospital, [name]. Ibadan, the capital of Oyo state is a highly populated city located in the rain forest belt of south-western Nigeria. Malaria transmission is intense and occurs all year round in the study area. The total population of Oyo state is estimated to be about 5.5 million with about 3.8 million people in

Ibadan alone. Ibadan has a land mass of 28,245.26 km. Oni Memorial Hospital serves a mix of urban and rural populations as rural patients are referred to it, though more of its patients are from the urban populations.

3.4 Timing and Duration of Study

The study will be conducted during the high malaria transmission season, from April 2019 to September 2019.

3.5 Study Population

The study population will consist of patients with uncomplicated *P. falciparum* malaria attending the study hospital who are aged between 3 and 144 months of age.

3.6 Sample Size Calculation

$$n = \frac{(Z_{1-\alpha} + Z_{1-\beta})^2 [P_1(1-P_1) + P_2(1-P_2)]}{[\varepsilon - (P_1 - P_2)]^2}$$

For Ref – Chow et al, 2008 (see

attachment)

Where

$Z_{1-\alpha}$ = standard normal deviate for level of significance; at $\alpha=0.05$, it is 1.96

$Z_{1-\beta}$ = standard normal deviate for power (1- β); at $\beta=0.2$ (80% power), it is 0.84 but at $\beta=0.1$ (90%), it is 1.28

P_1 : 28-day cure rate in AL = 96.4%

P_2 : 28-day cure rate in PA = 98.9%

ε : non-inferiority margin= 5%

Applying the formula and parameters above, sample size for each group

90% power: 70 per group [total 140]

80% power: 51 per group [total 102]

Assuming a difference of 2.5% in cure rate between PA and AL (98.9% vs 96.4%) [REF- Roth et al, 2018], 140 patients are required to be 90% sure that the upper limit of a one-sided 95% confidence interval will exclude a difference in favor of the standard group of more than 5%

Total N = 140. Allowing for 20% loss to follow up, the total number of patients required would be 168 to give 84 patients per arm. (See sample size calculation attachment)

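### Section 3.6 prints 1.96 for Z(1-alpha), but the stated 70 and 51 per group follow from 1.645; with 1.96 the formula gives 86 and 64

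*Combined protocol and SAP*

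**What the plan says.** Section 3.6 uses a non-inferiority formula for two proportions. The significance level enters as Z(1-alpha), not Z(1-alpha/2). The deviate is defined as "standard normal deviate for level of significance; at $\alpha=0.05$, it is 1.96". The power deviates are 0.84 (80%) and 1.28 (90%). The assumed 28-day cure rates are 96.4% for artemether-lumefantrine (P1) and 98.9% for pyronaridine-artesunate (P2), and the margin is 5%.

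The results are introduced with "Applying the formula and parameters above, sample size for each group" and are given as "90% power: 70 per group [total 140"] and "80% power: 51 per group [total 102"].

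The same section then states the criterion that the 140 patients should meet with 90% probability: "the upper limit of a one-sided 95% confidence interval will exclude a difference in favor of the standard group of more than 5" (in percentage points). It adds 20% for loss to follow-up, giving 168 patients, or 84 per arm.

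The Data Analysis section says "Proportions of treatment outcome will be compared by using chi square" and sets P < 0.05 as the threshold for significance. It gives no level, sidedness or confidence limit for the non-inferiority comparison.

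**The concern.** At alpha = 0.05, Z(1-alpha) is 1.645. The value 1.96 belongs to a one-sided 2.5% test or, equivalently, a two-sided 95% interval. Section 3.6 therefore pairs a deviate for one criterion with a confidence-limit statement for another, and says that sizes which fit only the second were obtained with the first.

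Two things are at stake. First, anyone who puts the printed parameters into the printed formula gets different sample sizes. Second, the deviate determines which confidence limit must clear the 5% margin. Someone who takes the printed 1.96 at face value, or reads P < 0.05 in Data Analysis as two-sided, would apply a stricter limit than the one the sizes were built on. That choice can change the conclusion of the primary comparison, so it should be fixed in writing before the data are seen.

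**Working it through.** **Inputs, all from section 3.6:** P1 = 0.964, P2 = 0.989, margin = 0.05, Z(1-beta) = 1.28 or 0.84, printed Z(1-alpha) = 1.96, equal groups.

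**Common factor**

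- Variance sum: 0.964 × 0.036 + 0.989 × 0.011 = 0.034704 + 0.010879 = 0.045583.
- Squared distance: [0.05 − (0.964 − 0.989)]² = 0.075² = 0.005625.
- Ratio: 0.045583 / 0.005625 = 8.1036.
- Hence n per group = (Z(1-alpha) + Z(1-beta))² × 8.1036.

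**Reproducing the plan's sizes**

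| Z(1-alpha) | 90% power (1.28) | 80% power (0.84) |
|---|---|---|
| 1.645 | 2.925² × 8.1036 = 69.33, so 70 | 2.485² × 8.1036 = 50.04, so 51 |
| 1.96 | 3.24² × 8.1036 = 85.07, so 86 | 2.80² × 8.1036 = 63.53, so 64 |
| Section 3.6 | 70 | 51 |

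Both printed sizes match 1.645 and neither matches 1.96. In total, 1.96 would need 172 and 128 patients, against the printed 140 and 102.

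**Solving backwards for the deviate**

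- A size that rounds up to 70 at 90% power needs Z(1-alpha) between √(69/8.1036) − 1.28 = 1.638 and √(70/8.1036) − 1.28 = 1.659.
- A size that rounds up to 51 at 80% power needs Z(1-alpha) between √(50/8.1036) − 0.84 = 1.644 and √(51/8.1036) − 0.84 = 1.669.
- Both hold together only from about 1.644 to 1.659. That range contains 1.645 and is far from 1.96.

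Other readings were tried: unrounded deviates, pooled variance, equal cure rates in both arms, the opposite sign of the difference, and a continuity correction. None that uses 1.96 gives 70 and 51.

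**Power under each reading:** power = Φ(√(n/8.1036) − Z(1-alpha)).

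| Evaluable per group | One-sided 95% limit (1.645) | One-sided 97.5% limit (1.96) |
|---|---|---|
| 51 | 80.6% | 70.8% |
| 67 (84 less 20%) | 89.1% | 82.0% |
| 70 | 90.2% | 83.6% |
| 84 (no loss) | 94.2% | 89.6% |

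At 70 per group, for example, √(70/8.1036) = 2.939. Then Φ(2.939 − 1.645) = Φ(1.294) = 0.902, and Φ(2.939 − 1.96) = Φ(0.979) = 0.836.

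**The case against.** The best reply is that this is one misprinted number. The formula uses Z(1-alpha), alpha is 0.05, the stated criterion is a one-sided 95% limit, and both sizes agree with 1.645. Only 1.96 is out of line. On that reading the sizes, power, enrolment and decision rule are all unaffected, and the lower powers are hypothetical because they require the confidence-limit sentence to be wrong as well. The section also refers to a sample-size attachment that is not among the documents available here, and the reference list includes an online non-inferiority calculator. Either may have used the right level.

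Much of this stands. The one-sided 95% sentence is the only written success criterion and it favours 1.645, so this point does not show an underpowered trial. The lower powers apply only if 1.96 is intended.

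It does not remove the error. The section says that the printed parameters produce the printed sizes, and no attachment can make 1.96 do that. Nor is the criterion repeated where the analyst would look for it, because Data Analysis gives only a chi-square comparison and a P-value threshold. The absence of a non-inferiority analysis there is a larger and separate matter. It is relevant here only because that section cannot resolve the conflict.

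The power at full enrolment also depends on the enrolment figure. The protocol's opening summary plans 162 children (81 per arm) rather than 168. With all 81 evaluable, power is 93.5% under 1.645 and 88.5% under 1.96. This does not affect the conflict over the deviate.

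**Conclusion.** The point holds. The printed deviate of 1.96 is inconsistent with the formula's own term at alpha = 0.05, with the one-sided 95% limit, and with both stated sample sizes. It is most likely the wrong figure, and 1.645 the value used.

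If a one-sided 5% level is intended, 70 and 51 per group are correct and give 90.2% and 80.6% power. If 1.96 is intended, the formula needs 86 and 64 per group, and the stated sizes give 83.6% and 70.8%. That is a loss of 6.6 percentage points at 70 per group (90.2 − 83.6) and 9.8 at 51 (80.6 − 70.8).

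These figures rest on the plan's own cure rates, margin and normal-approximation formula, taken as given. The correction should be made because the error sits in the sample-size derivation and leaves the decision limit open to two readings. It does not by itself call the planned size into question.

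**What to change.** Make the statements in section 3.6 agree, in one of two ways:

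1. **Correct the deviate (the likely intent).** Change Z(1-alpha) to 1.645 and state that the test is one-sided at 5% with a one-sided 95% confidence limit. The 70 and 51 per group and their stated powers stand.
2. **Keep 1.96.** Change the confidence-limit sentence to a one-sided 97.5% limit (two-sided 95% interval). Restate the power as about 84% for 70 evaluable per group and about 71% for 51, noting that 84 enrolled per arm less 20% leaves about 67 evaluable and 82.0% power. No extra enrolment is needed if that lower power is accepted. Holding 90% power would need 86 evaluable per group.

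Under either option, add a sentence to Data Analysis giving the same level and confidence limit for the non-inferiority comparison, before any outcome data are examined.

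The first option costs one corrected number with its level statement, and one added sentence. The second also changes the confidence-limit sentence and means reporting a less favourable power.

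### With about 2.5 and 0.8 expected failures per arm, the stated 90% power at 70 per group does not hold for a confidence limit with about 5% error: a score-type limit gives 86%, and the plan names no limit

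*Combined protocol and SAP*

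**What the plan says.** Section 3.6 (Sample Size Calculation) gives a two-proportion non-inferiority formula with the unpooled variance. Its inputs are AL cure 96.4%, PA cure 98.9% and a margin of 5 points. The result is "90% power: 70 per group [total 140", with 51 per group for 80% power. The promise attached to the 140 patients is that the "upper limit of a one-sided 95% confidence interval will exclude a difference in favor of the standard group of more than 5" percentage points. The deviate printed for alpha is described as "standard normal deviate for level of significance; at $\alpha=0.05$, it is 1.96". An allowance for 20% loss then raises the total to 168, or 84 per arm. The opening summary gives an enrolment of 162.

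The Data Analysis section says "Proportions of treatment outcome will be compared by using chi square", with P < 0.05 as the threshold. Neither section says how the confidence limit for the difference in cure rates is to be calculated.

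**The concern.** The formula treats the difference in observed cure rates as normal, with a variance estimated separately in each arm. That works poorly when an arm has two failures, one, or none: the estimated variance becomes very small, or zero if every child in both arms is cured. The limit then looks more precise than it is.

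The statement in Section 3.6 pairs 90% power with a one-sided 5% error. If the analysts use the limit the formula implies, a PA that is truly 5 points worse will be declared non-inferior more often than stated. If they use a limit that holds the error near 5%, the power is lower than stated. With no method named, the choice could be made after one or two failures have been seen, when it can decide the conclusion.

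**Working it through.** **Inputs (all from Section 3.6).** AL 0.964, PA 0.989, margin 0.05, 70 evaluable per arm, one-sided 95% limit, normal deviates 1.28 (90% power) and 0.84 (80%).

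**1. Reproduce the plan's figure.** n = (z_alpha + z_beta)² × [P1(1−P1) + P2(1−P2)] / [margin − (P1−P2)]².

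- Variance term: 0.964 × 0.036 + 0.989 × 0.011 = 0.045583.
- Denominator: (0.05 + 0.025)² = 0.005625.
- z = 1.645: (1.645 + 1.28)² × 0.045583 / 0.005625 = 69.3, so 70. At 80% power, 50.04, so 51. Both match.
- z = 1.96 as printed: 85.1, so 86. At 80% power, 63.5, so 64. Neither matches.

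The plan's numbers therefore rest on 1.645, which agrees with its one-sided 95% statement. The printed 1.96 does not.

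**2. Expected failures.** AL: 70 × 0.036 = 2.52. PA: 70 × 0.011 = 0.77.

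**3. Exact operating characteristics at 70 per arm.** For every pair of cure counts, note whether the one-sided 95% upper limit for AL minus PA falls below 0.05, and sum the binomial probabilities of the pairs where it does. Power uses 96.4% vs 98.9%. Error sets PA 5 points below AL.

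| Limit | Power | Error, AL 96.4% / PA 91.4% | Error, AL 98.9% / PA 93.9% |
|---|---|---|---|
| Wald (unpooled, matches the formula) | 92.8% | 7.1% | 9.2% |
| Score-type (Farrington-Manning, Miettinen-Nurminen, Newcombe: identical here) | 86.0% | 4.7% | 4.8% |

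The second error column assumes that AL cures as well as the plan expects PA to, which is the upper of its two rates.

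**4. The choice can change the conclusion.** Take AL 70/70 and PA 69/70.

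- Wald: difference 1/70 = 0.0143; standard error √(0.9857 × 0.0143 / 70) = 0.0142; upper limit 0.0143 + 1.645 × 0.0142 = 0.038, below 0.05, so non-inferior.
- Farrington-Manning: the restricted estimates are AL 1.00 and PA 0.95; standard error √(0.95 × 0.05 / 70) = 0.0260; statistic (0.05 − 0.0143) / 0.0260 = 1.37, below 1.645, so not shown.

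**5. Score-limit power at other evaluable numbers.**

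| Evaluable per arm | Where it comes from | Score power |
|---|---|---|
| 67 | 84 × 0.8 = 67.2 | 78.5% |
| 70 | Section 3.6 | 86.0% |
| 81 | 162 / 2, no loss | 86.6% |
| 82 | smallest number reaching 90% | 90.4% |
| 84 | 168 / 2, no loss | 90.4% |

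Power moves in jumps because the counts are small whole numbers.

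**The case against.** The plan never prescribes a Wald interval. Sizing a trial with an unpooled formula does not commit the analysis to that limit, and Section 3.6 points to an attachment that is not available here. That stands: the inflated error is conditional on the analysts using the limit the formula implies. The gap in the plan is that no limit is named.

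Nor is 70 per group a slip of arithmetic. It reproduces, and for its own Wald limit the formula slightly understates power (90% planned, 92.8% exact). The shortfall appears only once a limit with about 5% error is required.

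The 86% belongs to exactly 70 evaluable per arm. With all 84 followed, a score limit does reach 90%. Score limits are also not strict: for AL cure rates of 90% to 100% the error reaches 5.2% at 67 per arm and 5.25% at 84. It is therefore right to say about 5%, not at most 5%.

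A reader might infer two stronger things. One is a Wald error of 11% or more. That needs an AL cure rate near 99.7%, which the documents do not give; their two rates support 7% to 9%. The other is power as low as 63%, which results from using the printed 1.96 with a score limit at 70 per arm. That combines the z inconsistency with the small-count problem and is not the effect of few failures alone.

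**Conclusion.** The concern holds in a limited form. At the plan's own cure rates and 70 evaluable per arm, none of the limits checked delivers both the stated 90% power and the stated 5% one-sided error. The Wald limit exceeds the power but has 7% to 9% error. The score-type limits hold the error near 5% and give 86% power, about 4 points short. The chi-square comparison does not fill the gap, because it tests equality and not a 5-point deficit; a non-significant result would not show non-inferiority.

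These figures assume the stated cure rates, equal arms and a one-sided 5% level. The 86% should not be read as the trial's power whatever the follow-up: on the plan's own enrolment and loss figures, the range is 78.5% to 90.4%.

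**What to change.** - In the Data Analysis section, state that non-inferiority is judged from a one-sided 95% upper limit for the AL minus PA cure rate against 5 points, and name one score-type method (Farrington-Manning, Miettinen-Nurminen or Newcombe). Any chi-square comparison is then supplementary; with so few failures, Fisher's exact test suits it better.
- In Section 3.6, restate the power as about 86% at 70 evaluable per arm. Add that exact power is about 79% at 67, 87% at 81 and 90% at 82 to 84.
- Reconcile the printed 1.96 with the one-sided 95% statement, since 70 and 51 per group need 1.645.

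The cost is wording, a different software routine for the limit, and a stated power about 4 points lower. If the sponsor prefers to keep 90%, the plan needs at least 82 evaluable per arm. With 20% loss that is 82 / 0.8 = 102.5, so 103 enrolled per arm, or 206 in total against the present 168.
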